Name of Finished Pr	oduct:		
SB204			
Name of Active Ingre	edient:		
NVN1000			
Title	A Phase 3 Multi-Center, Open Label Study Evaluating the Long Term		
	Safety of SB204 Once Daily in the Treatment of Acne Vulgaris		
Study Objectives	The primary objective of this study is to evaluate the safety of SB204 4%		
	in subjects with acne vulgaris for up to 40 weeks of treatment.		
Treatment	Eligible subjects at the Baseline visit will be assigned to SB204 QD and		
Regimens	treated for up to 40 weeks to acne affected areas including the face, chest,		
	back and upper shoulders.		
Formulation	Investigational Drug: SB204, containing NVN1000 Gel and hydrogel		
Study Period	Subjects will be dosed in the study for up to 40 weeks.		
Study Design	This is a multi-center, open label long-term safety (LTS) study to be		
	conducted in approximately 600 subjects with acne vulgaris. Subjects		
	eligible to enroll in this study will have completed one of the Phase 3		
pivotal studies with SB204, NI-AC301 or NI-AC302.			
Subjects who satisfy the entry criteria at the Baseline visit will			
enrolled to receive open-label SB204. Investigational drug			
	delivered from a double barrel single pump dispenser. The pump		
dispenses product (NVN1000 Gel and a hydrogel) from to			
	which will be mixed together quickly (about 5 seconds) by the subject		
	and applied to the acne affected areas including the face, chest, back and		
	upper shoulders once daily. No other acne treatments will be permitted		
	during the study. Tolerability and safety assessments include cutaneous		
	tolerability evaluation, adverse event collection, physical exams		
	including blood pressure and pulse rate, and urine pregnancy tests		
	(UPTs). Subjects will return for post-baseline evaluation at Weeks 4, 12,		
	24, 36 and 40.		
Diagnosis and	Male and female subjects who completed one of the two SB204 Phase 3		
Criteria for	pivotal studies will be eligible for participation in the study. The last visit		
Inclusion/Exclusion	in the Phase 3 pivotal study may serve as the first visit for the long-term		
	safety study. Subjects must enroll in the LTS study within 7 days of		
	completion of NI-AC301 or NI-AC302. Any subject who terminated		
	early from one of these studies for any reason will not be eligible to enroll		
	taily from one of these states for any reason will not be engine to enfor		

in this long-term safety study. Inclusion criteria: • Have no more than two nodules on the face; Completed 12 weeks of treatment in NI-AC301 or NI-AC302 Exclusion Criteria: Terminated early from an SB204 Phase 3 pivotal study for any reason; • Have any dermatological conditions on the face that could interfere with clinical evaluations such as acne conglobata, acne fulminans, acne secondary to medications or other medical conditions, perioral dermatitis, clinically significant rosacea, or gram-negative folliculitis; • Have an on-going adverse event at the Week 12 visit for NI-AC301 or NI-AC302 that warrants stopping study drug application; • Have facial hair, tattoos or other facial markings that would interfere with efficacy and safety assessments; • Have any underlying disease(s) or some other dermatological condition of the face that requires the use of interfering topical or systemic therapy or makes evaluations and lesion count inconclusive; • Have used medications or vitamins during the 12 weeks immediately preceding Baseline which are reported to exacerbate acne (e.g. azathioprine, haloperidol, halogens such as iodides or bromides, lithium, anabolic steroids, systemic corticosteroids, phenytoin and phenobarbital). Daily use of a multi-vitamin is acceptable. Approximately 600 subjects will be entered into the study. **Sample Size** Safety and tolerability assessments will be collected beginning at the Safety and Baseline visit for NI-AC303. The subject must enroll in NI-AC303 **Tolerability Evaluation** within 7 days of completion of NI-AC301 or NI-AC302. Demographics and the subject's Week 12 visit values from NI-AC301 or NI-AC302 for blood pressure, pulse, urine pregnancy test, physical exam findings, lesion counts and tolerability will be used as the Baseline values for NI-AC303. Adverse events will be assessed and collected at each evaluation beginning at Baseline. A brief physical exam will be collected at Week 40/Early Termination (ET). Blood pressure and pulse will be collected at each visit through Week 40/ET. Urine pregnancy tests in women of

	child-bearing potential (WOCBP) will be conducted at each visit.
	Subjects will be assessed at each visit through Week 40 for cutaneous tolerability on the face. Tolerability will be assessed on a scale of 0 to 3 where 0=none, 1=mild, 2=moderate, and 3=severe for erythema, scaling, dryness, pruritus, and burning/stinging. The body surface area (BSA) treated (based on locations) will be collected at each visit for each subject Extent of exposure will be calculated for each subject based on the number of treatments and treatment area. Extent of exposure will also be summarized on a unit day which will be defined as total exposure divided by the total number of days enrolled.
Endpoints	Safety endpoints will include adverse events, changes in physical
	examination and changes in vital sign measurements. Any clinically significant changes noted during the physical exam as well as from the vital sign measurements will be recorded as adverse events and included in the comparison. Urine pregnancy tests in women of child-bearing potential will be conducted at each visit.
	Tolerability endpoints will include the investigator's assessment of erythema, scaling, dryness, and the subject's report of pruritus and burning/stinging based on the preceding 24 hours.
Statistical Methods	All statistical processing will be performed using statistical analysis software (SAS®) unless otherwise stated. Safety analyses will be performed using the safety population.
	Safety Analyses
	Adverse Events
	All AEs occurring during the study will be recorded and classified on the basis of the Medical Dictionary for Regulatory Authorities (MedDRA) terminology. Descriptions of AEs will include the date of onset, the date the AE ended, the severity of the AE, the relationship to study medication, and the outcome. All reported AEs that occurred on or after the Baseline date will be included in the summaries and analysis. Summaries will be presented to describe the characteristics of the adverse events reported and will include the number and percentage of subjects who report at least one AE and the number of events reported by severity, seriousness, and relationship to study medication. A
	summary of adverse event system organ class (SOC) and preferred terms (PTs) will also be presented. A subject will be counted only once under

each SOC and PT. For the summary by severity, subjects will only be counted once for a specific SOC or PT under the worst severity. For the summary by relationship to study medication, subjects will only be counted once for a specific SOC or PT under the highest relationship.

If multiple serious adverse events (SAEs) are reported, a table summarizing the SAEs characteristics will be provided.

All information pertaining to AEs noted during the study will be listed by subject, detailing verbatim given by the Investigator, preferred term, system organ class, start date, stop date, severity, seriousness, and relationship to study medication. The AE onset will also be shown relative (in number of days) to the day of initial dose of the open label study medication. A summary of adverse events that lead to a subject's discontinuation of study medication usage will also be provided.

Physical Examinations

Any clinically significant changes from Baseline will be documented as an AE.

Vital Signs

Blood pressure and pulse will be summarized from Baseline through Week 40. Additionally, change from Baseline in vital signs will be summarized at Weeks 4, 12, 24, 36 and 40. Clinically significant changes from Baseline will be documented as an AE.

Urine Pregnancy Tests

Urine pregnancy test results for WOCBP will be presented in data listings by subject.

Tolerability Analyses

Cutaneous tolerability assessments (erythema, scaling, dryness, pruritus, burning/stinging) will be summarized with frequency counts and percentages at each evaluation.

LIST OF ABBREVIATIONS AND DEFINITIONS OF TERMS

Abbreviation	Definition		
AE	Adverse Event		
BSA	Body Surface Area		
EDC	Electronic Data Capture		
ET	Early Termination		
FDA	Food and Drug Administration		
GCP	Good Clinical Practice		
ICH	International Conference on Harmonisation		
IRB	Institutional Review Board		
IUD	Intrauterine Device		
MedDRA	Medical Dictionary for Regulatory Activities		
NOVAN	Novan, Inc.		
OTC	Over-the-Counter		
PT	Preferred Term		
SAE	Serious Adverse Event		
SAP	Statistical Analysis Plan		
SAS	Statistical Analysis Software		
SOC	System Organ Class		
SOP	Standard Operating Procedure		
TEAE	Treatment Emergent Adverse Events		
UPT	Urine Pregnancy Test		
WOCBP	Women of Child-Bearing Potential		

TABLE OF CONTENTS

IN	FOR	MATION PAGE	3
IN	VES	TIGATOR'S AGREEMENT	4
PF	OTO	OCOL SYNOPSIS	5
LI	ST O	F ABBREVIATIONS AND DEFINITIONS OF TERMS	9
$\mathbf{T}A$	BLE	OF CONTENTS	10
		F FIGURES	
		F TABLES	
		RODUCTION	

1. INTRODUCTION

1.1 BACKGROUND

Acne vulgaris is a chronic skin disease characterized by open and closed comedones, papules, pustules, and cysts. Current acne therapies include oral and topical antibiotics, topical keratolytics, and oral contraceptives.

Nitric oxide is a free radical gas naturally produced by the human body which has antimicrobial and anti-inflammatory activity. Novan, Inc. has developed a topical gel containing NVN1000, a drug which releases nitric oxide to the skin after topical application. SB204, an admixture of an alcoholic NVN1000 Gel with an aqueous hydrogel, is in development for the treatment of acne vulgaris. In randomized, double-blind, placebo-controlled, 12-week, Phase 2 studies, treatment with SB204 decreased inflammatory and non-inflammatory lesion counts and improved the Investigator Global Assessment (IGA) in subjects with acne and was well tolerated.

To date, approximately 400 subjects have been treated with NVN1000 Gel, including SB204, and approximately 200 subjects have been treated with the Vehicle Gel.

1.2 INVESTIGATIONAL PRODUCT

SB204 is an alcohol-based topical gel containing NVN1000 and the formulation will be dispensed from a dual chamber pump with hydrogel.

Investigational Product				
Name of Active Ingredient	NVN1000			
Drug Name/Concentration	SB204 4%			
Manufacturer	Ei, LLC			
Packaging	Pump designed to deliver 1:1 Hydrogel: NVN1000 Gel to yield final concentration of SB204 4%			
Storage Requirements	Refrigerated, 2-8 °C until dispensed.			
Appearance Post-Mixing	Opaque white gel			
Dosing Schedule	Once daily			
Route of Administration	Topical Application			

1.3 NONCLINICAL STUDIES WITH NVN1000 GEL

Novan has conducted over 30 nonclinical studies to evaluate the local safety and tolerance of NVN1000 (drug substance and formulated product) following dermal administration to support the acne development program. Repeat dose dermal toxicology studies have included 4-week and 13-week GLP dermal toxicology studies in miniature swine, and a 13-week dermal toxicology study in both rats and mice. A 39-week miniature swine study has completed the in-life portion; data from that study will be available prior to initiation of this long-term safety study. In completed studies in both the miniature swine and mice, doses of NVN1000 far in excess in both concentration and applied surface area of projected clinical doses have not demonstrated any significant toxicological effects. The most relevant and persistent finding has been a transient dermal erythema that is concentration dependent and believed to be a consequence of a vascular dilation, "flushing" effect. Additional safety studies in rabbits and guinea pigs showed no effects on acute dermal irritation or skin sensitization. As expected, due to the alcohol-based formulation, NVN1000 was found to be an ocular irritant. From a genotoxicity perspective, NVN1000 was positive in a standard in vitro AMES assay but negative in three in vivo mutagenicity assays. Additionally, in SEG I and II reproductive toxicology studies in rats and rabbits, oral administration of NVN1000 resulting in high systemic levels of nitrate and hMAP3, a key structural component of NVN1000, showed the requisite maternal toxicological effects upon dose escalation as a complication of high methemoglobin concentrations, but minimal effects on fertility or fetal development.

For additional information refer to the Investigator's Brochure.

1.4 CLINICAL STUDIES WITH NVN1000 GEL

The topical administration of NVN1000 Gel to healthy volunteers or subjects with acne vulgaris has generally been well-tolerated with no safety concerns identified. In nine completed clinical studies, approximately 400 subjects have been treated with NVN1000 Gel or SB204 and approximately 200 subjects have been treated with Vehicle Gel. One unrelated SAE has been reported and the systemic AE profile has been similar in subjects treated with active (NVN1000 Gel or SB204) and vehicle in the acne development program. Asymptomatic, transient erythema has been observed in some subjects. There have been no clinically significant changes in laboratory results including methemoglobin, or changes in physical examinations.

A cross-over pharmacokinetic (PK) study was conducted in 18 subjects with moderate to severe acne. Subjects were randomized to treatment with SB204 8% or Vehicle Gel to the face, chest, upper back, and shoulders (~17% BSA) in two treatment periods. In this study, there was no detectable plasma hMAP3 (LLOQ 5 ng/ml), a component of NVN1000 and no difference in plasma nitrate levels in subjects treated with SB204 versus Vehicle Gel. One subject withdrew during the second dosing period due to contact dermatitis. A 4 period, double-dummy, cross-over study in subjects with moderate to severe acne is ongoing to assess effects of therapeutic and

supratherapeutic doses of SB204 on ECG parameters. The thorough ECG study will be completed prior to dosing in the Phase 3 pivotal program.

In the Phase 2 clinical development program, the topical application of SB204 in subjects with acne vulgaris resulted in significant decreases in inflammatory and non-inflammatory lesion counts and improvement in the Investigator Global Assessment (IGA) when compared to vehicle. Once daily treatment was as effective as twice daily treatment.

A summary of the clinical studies conducted to date in subjects with acne is in the Investigator's Brochure.

1.5 SUMMARY OF BENEFITS AND RISKS

The pathogenesis of acne vulgaris includes several mechanisms which are potential targets for nitric oxide. Nitric oxide has been demonstrated to inhibit several inflammatory pathways relevant in acne, decrease *P. acnes*, and decrease sebum production. In two completed Phase 2 studies, SB204 4% administered in subjects with acne decreased inflammatory and non-inflammatory lesion counts at the end of treatment and improved IGA scores. Once daily treatment was as effective as twice daily treatment. In the studies conducted to date, the systemic AE profile was similar between subjects treated with NVN1000 Gel, SB204, and subjects treated with Vehicle Gel. SB204 4% has been generally well tolerated and has not been associated with a safety or tolerability signal. In PK studies, there was no detectable systemic exposure to the parent compound, NVN1000, or changes in plasma nitrate.

Dermal toxicology studies in mice and minipigs have demonstrated minimal evidence of toxicity with mild-moderate dermal changes most frequently reported. In reproductive toxicology studies, findings were limited to toxicities associated with high methemoglobinemia at supra-therapeutic doses.

Based on the known mechanism of action of nitric oxide, theoretical risks from systemic exposure following topical administration of NVN1000 Gel or SB204 include hypotension and headache. Methemoglobin has been monitored in previous clinical studies with NVN1000 Gel and SB204 and no significant changes in methemoglobin levels have been observed.

Inadvertent administration to the eyes may result in ocular irritation due to the excipients and should be avoided. Should the product be accidently instilled in the eye(s), prompt flushing with copious amount of normal saline or water is recommended.

A transient (approximately 5-10 minutes), asymptomatic erythema has been observed in some subjects shortly after application of NVN1000 Gel or SB204 which is a physiologic response (vasodilation) to local nitric oxide release. Topical application has been associated with local application-site reactions including erythema, scaling, dryness, and burning/stinging. These local

application-site reactions may occur due to the active agent (NVN1000) or the vehicle. In other development programs, local application-site reactions that led to treatment discontinuations were observed following application of alcoholic NVN1000 Gel or Vehicle Gel under occlusion in subjects with psoriasis or to the genital/perianal area in subjects with genital/perianal warts.

Based on available data, Novan anticipates that the risks to subjects enrolling in this Phase 3 study at which the maximum strength of SB204 will be 4% once daily on up to 17% body surface area are minimal, and that appropriate monitoring is in place to assess safety. Some subjects may have a clinical benefit in this long-term, open label study.

2. RATIONALE AND OBJECTIVES

2.1 STUDY RATIONALE

Novan is conducting this study to evaluate the long term safety of SB204 4% administered once daily. Subjects will dose once daily for up to 40 weeks (280 days) with SB204 4% to acne affected areas. Based on the previous human safety data with SB204 at up to 8% and Vehicle Gel as well as the nonclinical safety data including dosing with and without hydrogel, this dose is expected to be safe and well tolerated.

[figure not shown]
2.2 STUDY OBJECTIVES

The primary objective of this study is to evaluate the long term safety of SB204 4% once daily for up to 40 weeks in subjects with acne vulgaris.

3. STUDY DESIGN

Figure 1 depicts the overall study design for this 40-week, open label study in subjects with acne vulgaris dosed once daily with SB204 4%. Subjects must have completed participation in one of the pivotal acne trials (NI-AC301 or NI-AC302) to be eligible to participate in this long term safety trial. Subjects will be treated chronically or repeatedly as recommended by the Investigator for up to 40 weeks. The Investigator may stop treatment if the subject's acne is in remission and re-initiate treatment if the subject's acne recurs. Any subject who is determined to be clear will remain enrolled in the study until study completion or termination. The total time on study will be counted as the days from enrollment until the subject discontinues or the study terminates.

Figure 1: Study Diagram

3.1 STUDY ENDPOINTS

3.1.1 SAFETY ENDPOINTS

Safety endpoints will include adverse events, changes in physical examination and changes in vital sign measurements. Any clinically significant changes noted during the physical exam as well as from the vital sign measurements will be recorded as adverse events and included in the comparison. Urine pregnancy tests in women of child-bearing potential will be conducted at each visit.

3.1.2 TOLERABILITY ENDPOINTS

The cutaneous tolerability assessments include the investigator's assessment of erythema, scaling, dryness, and the subject's report of pruritus and burning/stinging based on the preceding 24 hours.

3.1.3 EXTENT OF EXPOSURE

Extent of exposure will be calculated based on total number of days of study drug application and the body surface area treated (face, upper back, upper chest/shoulders).

3.1.4 EFFICACY ENDPOINTS

Efficacy endpoints will include change in inflammatory and non-inflammatory lesion counts from baseline at each study visit.

3.2 STRUCTURE

This is a multi-center, open label study. Eligible subjects will have completed either NI-AC301 or NI-AC302, regardless of which treatment arm they were assigned to receive in the original study.

3.3 DURATION

Subjects will be in the study for a maximum of 40 weeks; the Week 12 visit from the pivotal study will serve as the Baseline Visit for this study.

3.4 DOSAGE/DOSE REGIMEN

SB204 will be dispensed from a dual-chamber pump designed to deliver approximately equal amounts of NVN1000 Gel and hydrogel. NVN1000 Gel will be opaque and the hydrogel will be clear. The subject will instantly mix the two substances in the palm of the hand and then immediately massage a thin layer over the acne affected areas once daily after washing. The product should be mixed for about 5 seconds until thoroughly combined with a uniform opaque appearance then applied with the fingertips. Subjects should apply SB204 prior to bedtime.

Up to 2.7 g of SB204 4% will be applied evenly over the acne affected area, including the face, chest, back, and upper shoulders once a day for a period of up to 40 weeks (280 days). The amount of SB204 per application will vary depending on the areas to be treated as shown in Table 1 below. One pump stroke (0.9 g) will be used for the face. Application to the face, upper back and upper chest/shoulders will require up to 2.7 g (three (3) pump strokes).

Table 1: Dosing Amount by Area

Area (BSA)	Number of Pump Strokes	Amount of Product	
Face (3%)	1	0.9 g	
Upper Back (6%)	1	0.9 g	
Upper Chest/Shoulders (8%)	1	0.9 g	

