#### 3.5 Populations

#### 3.5.1 Safety Population

The safety population (SAF) will include all subjects that have received at least one dose of SB204. For the summaries, we are defining two subject categories, based on the subject's status at the start of the LTS:

- SB204 Experienced: subjects allocated to SB204 in the previous study
- SB204 Naïve: subjects allocated to vehicle in the previous study

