### 4.4 Extent and Duration of Exposure

Summaries of the duration of exposure, days of exposure, and extent of exposure (calculated total grams) to study drug will be presented, overall and by whether previously randomized to SB204 (SB204 experienced) or randomized to Vehicle (SB204 naïve). This information plus study drug management details will be listed as well. All exposure endpoints will take into account whether the subject received SB204 in the previous study (NI-AC301 or NI-AC302).

Duration of exposure will be defined as:

Date of Last Drug Administration – Date of First Drug Administration + 1 day

Where date of first drug administration is the date of first treatment in the previous pivotal study for subjects randomized to SB204 in the previous study, and date of first dose in the LTS for subjects randomized to vehicle in the previous study.

Days of exposure will be defined as the total number of days that the subject reported taking study medication, and includes the days of exposure to SB204 in the previous study (NI-AC301 or NI-AC302) if applicable.

Extent of exposure will be based on the number of areas treated (face, upper back, and/or upper chest/shoulders, and any other areas reported) and the number of days with treatment. For subjects randomized to SB204 in the previous studies, drug was only applied to the face so for the days of exposure from the previous studies, it will be assumed that there is only one area of application, i.e. the face.

Each application is equal to 0.9 g. Extent of exposure is estimated as the sum of application areas (face only=1, face and chest=2, etc.) times the number of days of application to those areas times 0.9g. For example, a subject who applies 200 applications to the face only will have extent of exposure = 180g, while a subject who applies 100 applications to the face and 50 applications to the upper back will have extent of exposure = 135 g. The maximum extent of exposure would be: [0.9 grams x number of days on treatment in previous study] + [0.9 grams x 4 areas x number of LTS days on treatment]. Most subjects will have less exposure than this, so extent of exposure will be categorized logically depending on actual distribution of subjects. Initially, quartiles will considered.

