#### 4.5 Safety

#### 4.5.1 Adverse Events

All AEs that occur during the study or continue after enrollment into this study will be recorded and classified on the basis of Medical Dictionary for Regulatory Activities (MedDRA) terminology version 18.1. Adverse events ongoing at end of the pivotal study will be carried forward to this study, will not be considered treatment-emergent for this study, and will be summarized separately by SOC, PT, and relatedness. Treatment-emergent AEs (TEAEs) will be defined as AEs reported on or after the first day of enrollment in this long term safety study.

All information pertaining to an AE noted during the study will be listed by subject, detailing verbatim term given by the Investigator or designee, preferred term, system organ class (SOC), onset date, resolution date, severity, seriousness, action taken, outcome, and drug relatedness. The event onset will also be shown relative (in number of days) to date of first dose in this study.

Treatment-emergent AEs will be summarized by the number of subjects reporting a TEAE, SOC, preferred term, severity, relationship to study drug (causality), and seriousness. When summarizing AEs by severity and relationship, each subject will be counted only once, within a system organ class or a preferred term, by using the event with the highest severity and greatest relationship within each classification.

Serious AEs will be summarized by severity, and relationship to study drug, and individual SAEs will be listed by subject. In addition, a list of subjects who prematurely discontinue study drug due to an AE, had AEs leading to treatment modification, and AEs that resulted in death will be provided.

Adverse events will also be summarized by windows of duration of exposure to study drug to determine if there is a safety signal due to duration of exposure. The windows of exposure will include but are not limited to: 1) within the first 24 hours (i.e. Day 1 of the LTS study), 2) up to 1 month (i.e. 2-30 days), 3) up to 3 months (i.e. 31-90 days), 4) up to 6 months (i.e. 91-180 days) and 5) up to 12 months (i.e. 181-365 days).

Adverse event incidence will also be summarized by the extent of exposure categories (in grams) as described in section 4.4.

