Treatment Emergent Adverse Events (TEAE) by System Organ Class, Preferred Term, and Duration of Exposure Safety Population

System Organ Class Preferred Term	Within 24 hours (N=XXX)	Within 2-30 days (N=XXX)	Within 31-90 Days (N=XXX)	Within 91-180 Days (N=XXX)	Within 181-365 Days (N=XXX)	Overall (N=XXX)
Number of Subjects with at Least One TEAE Number of Events	xx (xx.x)	xx (xx.x)	xx (xx.x)	xx (xx.x)	xx (xx.x)	xx (xx.x) xx
System Organ Class 1	xx (xx.x)	xx (xx.x)	xx (xx.x)	xx (xx.x)	xx (xx.x)	xx (xx.x)
Preferred Term 1	xx (xx.x)	xx (xx.x)	xx (xx.x)	xx (xx.x)	xx (xx.x)	xx (xx.x)
Preferred Term 2	xx (xx.x)	xx (xx.x)	xx (xx.x)	xx (xx.x)	xx (xx.x)	xx (xx.x)
System Organ Class 2	xx (xx.x)	xx (xx.x)	xx (xx.x)	xx (xx.x)	xx (xx.x)	xx (xx.x)
Preferred Term 1	xx (xx.x)	xx (xx.x)	xx (xx.x)	xx (xx.x)	xx (xx.x)	xx (xx.x)
Preferred Term 2	xx (xx.x)	xx (xx.x)	xx (xx.x)	xx (xx.x)	xx (xx.x)	xx (xx.x)

Note(s): Adverse event terms were coded using MedDRA dictionary version 18.1. Subjects are counted once within each level of summary. Duration of exposure is based on date of first dose of SB204, which could be in the previous study (NI-AC301 or NI-AC302).

Source: Listing xx.x.x.x, Program: xxxxx.sas, Output: T xx.x x x xxxx.rtf, Generated on: DDMMMYYYY HH:MM

Programmer Note: Order SOC by decreasing frequency and preferred term by decreasing frequency within SOC based on overall incidence.

Protocol Number: NI-AC303

Table 14.3.3.2.2

Treatment Emergent Adverse Events (TEAE) by System Organ Class, Preferred Term, and Extent of Exposure Safety Population

System Organ Class Preferred Term	1-100 grams (N=XXX)	>100-330 grams (N=XXX)	>330-675 grams (N=XXX)	>675 Grams (N=XXX)	Overall (N=XXX)
Number of Subjects with at Least One Event	xx (xx.x)	xx (xx.x)	xx (xx.x)	xx (xx.x)	xx (xx.x)
Number of Events	xx	xx	xx	xx	xx
System Organ Class 1 Preferred Term 1 Preferred Term 2	xx (xx.x)	xx (xx.x)	xx (xx.x)	xx (xx.x)	xx (xx.x)
	xx (xx.x)	xx (xx.x)	xx (xx.x)	xx (xx.x)	xx (xx.x)
	xx (xx.x)	xx (xx.x)	xx (xx.x)	xx (xx.x)	xx (xx.x)
System Organ Class 2 Preferred Term 1 Preferred Term 2	xx (xx.x)	xx (xx.x)	xx (xx.x)	xx (xx.x)	xx (xx.x)
	xx (xx.x)	xx (xx.x)	xx (xx.x)	xx (xx.x)	xx (xx.x)
	xx (xx.x)	xx (xx.x)	xx (xx.x)	xx (xx.x)	xx (xx.x)

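### The by-duration adverse event tables have two conflicting start points, and the one in the shell would place early trunk reactions of SB204 Experienced subjects after month one

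*Protocol*

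**What the plan says.** **Where drug is applied.** SAP 4.4 says of the pivotal studies: "For subjects randomized to SB204 in the previous studies, drug was only applied to the face". Protocol 3.4 widens the area in this study: "Application to the face, upper back and upper chest/shoulders will require up to 2.7 g (three (3) pump strokes". Below, trunk means the upper back and upper chest/shoulders.

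**Who is Experienced.** SAP 3.5.1 defines the group by earlier allocation, without regard to area: "SB204 Experienced: subjects allocated to SB204 in the previous study".

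**When the clock starts.** There are two answers.
- SAP 4.4 starts duration for Experienced subjects at the "date of first treatment in the previous pivotal study for subjects randomized to SB204 in the previous study". The footnote of Table 14.3.3.2.1 agrees: "Duration of exposure is based on date of first dose of SB204, which could be in the previous study". That shell is reused for every by-duration adverse event table through 14.3.3.11.1.
- SAP 4.5.1 equates the first window (24 hours) with Day 1 of the LTS. It gives the later windows as day ranges with no stated origin.

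**Purpose.** SAP 4.5.1 says the windows are there "to determine if there is a safety signal due to duration of exposure".

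**What else captures the trunk.** Cutaneous tolerability is scored on the face only (Protocol 4.1.1 to 4.1.3), so a trunk reaction can reach the tables only as an adverse event. Treated areas are recorded at every post-baseline visit.

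**The concern.** Local application-site reactions are the product's recognised risk (Protocol 1.5), and they are plausible soon after skin is first treated. For an Experienced subject, trunk skin is first treated in this study. If exposure is counted from the first facial dose about three months earlier, a reaction in the first weeks of trunk use is tabulated as one that arose after months of exposure.

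The by-duration tables pool Experienced and Naïve subjects and have no breakdown by area, so a reader could not see that this had happened. Early reactions would be understated and an apparent late onset could be produced, in the tables meant to answer the duration question. The study is descriptive, with no test or power calculation, so these tables are themselves the evidence.

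Because SAP 4.5.1 and the shell disagree, a programmer could follow either and report different tables from the same data.

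**Working it through.** **Plan's own figure.** One stroke is 0.9 g (Protocol 3.4), and 3 × 0.9 g = 2.7 g, as stated. In Protocol Table 1 the body surface is 3% + 6% + 8% = 17%, of which the trunk is 14 points (14/17 = 82%). SAP Table 1 lists chest and shoulders separately, giving 4 × 0.9 g = 3.6 g. That difference from the protocol must be reconciled, but nothing below depends on it.

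**Inputs for the clock.**
- Pivotal treatment: 12 weeks = 84 days (Protocol 3.5).
- Gap *g* from the pivotal Week 12 visit to LTS entry: 0 to 7 days (Protocol 3.5).
- Duration: last date − first date + 1 (SAP 4.4), applied here up to the event date.
- Windows: day 1, 2–30, 31–90, 91–180, 181–365 (SAP 4.5.1).
- Treatment-emergent events start at LTS enrollment (SAP 4.5.1).
- Assumptions: the pivotal Week 12 visit falls 84 days after first dose, and LTS drug starts on the day of entry.

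**Formula.** LTS day *k* of an Experienced subject is exposure day 84 + *g* + *k*. A day falls in 31–90 when *k* ≤ 6 − *g*.

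| Gap *g* | LTS Day 1 is exposure day | LTS days 1–30 in first two columns | in 31–90 | in 91–180 |
|---|---|---|---|---|
| 0 | 85 | 0 | 6 | 24 |
| 3 | 88 | 0 | 3 | 27 |
| 6 | 91 | 0 | 0 | 30 |
| 7 | 92 | 0 | 0 | 30 |

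**Sensitivity.** The documents do not give the pivotal visit window. If the visit fell on day 77, LTS Day 1 is exposure day 78 to 85; 6 to 13 of the first 30 LTS days fall in 31–90 and 17 to 24 in 91–180. If it fell on day 91, LTS Day 1 is exposure day 92 to 99 and all 30 fall in 91–180. The first two columns get none in any case.

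**The contradiction on one event.** A Day 1 event in an Experienced subject belongs in the 24-hour column under SAP 4.5.1. Under the footnote it belongs in 31–90 or 91–180.

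**Other end of the scale.** A 280-day course ends on exposure day 84 + *g* + 280 = 364 + *g*. With *g* of 2 or more it runs past day 365, to day 371 at most, beyond the last listed window.

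**LTS clock for comparison.** Counted from first LTS dose, days 1–280 divide into 1, 29, 60, 90 and 100 days across the five windows. Reactions in the first 30 days of trunk use fall in the first two columns if trunk use begins on LTS Day 1.

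**Denominators.** The shell gives an N per column but no rule for it. Under the first-ever-dose clock, Experienced subjects cannot have a treatment-emergent event in the first two columns. Counting them there would dilute the percentages.

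**Does another table recover it?** Protocol 7.7 foresees summaries by duration and by total body area exposed. The SAP's exposure categories are total grams, which mix area with days and include pivotal facial use. They do not isolate early trunk exposure.

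**The case against.** The strongest reply is that this is mainly an anchor problem. All the displacement comes from counting from the first-ever dose. Under an LTS clock, and with trunk use from LTS Day 1, it disappears. That stands. What remains is trunk use that starts later, and facial events, which an LTS clock would date too early for Experienced subjects.

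A first-ever-dose clock is also a legitimate measure of cumulative exposure. That stands too, and is a reason to keep it beside the LTS clock.

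Early onset is partly recoverable. SAP 4.5.1 promises onset relative to first LTS dose in a listing, Listing 16.2.8.1 carries start dates, Listing 16.2.6 shows areas by visit, and Table 14.3.3.1 splits events by Experienced/Naïve. But the Days item in Listing 16.2.8.1 is defined as event duration, and listings do not correct incidence tables.

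A reader might infer more than the documents support:
- *That the SAP settles on the first facial dose.* It does not; SAP 4.5.1 points to LTS Day 1.
- *That every early trunk reaction appears after three months.* With same-day rollover, LTS days 1–6 fall in 31–90, which SAP 4.5.1 labels as up to 3 months.
- *That the Experienced/Naïve contrast says nothing about trunk events.* Nothing in the documents shows that earlier facial use is irrelevant to trunk reactions.
- *That the number of displaced reactions can be estimated.* The Experienced share, the share treating the trunk and the reaction rate are not given. Protocol 4.2 also keeps tolerability findings out of adverse event reporting unless severe or leading to discontinuation, and whether that covers the trunk is unclear.

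**Conclusion.** The concern holds as an unresolved contradiction with a definite consequence under one reading. SAP 4.4 and the Table 14.3.3.2.1 footnote start the clock at the first pivotal dose, SAP 4.5.1 starts the first window at LTS Day 1, and the passages must be reconciled. If the footnote governs, no treatment-emergent event in an Experienced subject can enter the first two columns, and 24 to 30 of the first 30 LTS days fall in 91–180. Early trunk reactions in these subjects would then be shown as events after month one, mostly in 91–180.

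This rests on the SAP's statement that pivotal use was facial only and on the 84-day assumption. With the visit at day 77, at least 17 of the 30 days still fall in 91–180. It should be corrected before the tables are programmed. It affects how safety is described, not a hypothesis test.

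**What to change.** 1. In SAP 4.5.1 and the by-duration shells (14.3.3.2.1, 14.3.3.3.1 and on to 14.3.3.11.1), state the start of the clock explicitly and make SAP 4.4, 4.5.1 and the footnotes agree.
2. Present treatment-emergent events by days since first LTS dose beside days since first-ever SB204 dose, split by Experienced and Naïve. Limit each column's denominator to subjects who can contribute an event to that window, and extend the last window past day 365 on the first-ever-dose clock.
3. As a supplementary display, take subjects with a trunk area recorded by the time of onset. Tabulate their skin and application-site events by days from the start of the first LTS interval in which a trunk area was recorded.
4. Footnote that Experienced means earlier exposure of the face only.

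No new adverse event field is needed; areas and dates are already collected. A clock specific to the region of each event would go further, but it would require a data-collection change and is not needed to remove the main problem.

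The cost is SAP and shell wording, extra columns and one more display. The limitation is that the start of trunk use is known only to the visit interval: 4 weeks up to Week 4, 8 weeks (56 days) for Weeks 4–12, 12 weeks (84 days) for Weeks 12–24 and 24–36, and 4 weeks for Weeks 36–40. For trunk use beginning between Weeks 4 and 36 that is longer than the 30-day window, so the supplementary display should say so.
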